When investigating psychiatric comorbidity in BPD patients, focusing on anxiety and depression, has been the norm. However, important information on the relationship between other types of mental illness and back pain disorders might be identified, if a dataset of sufficient size and quality, is used for analysis. A population-based set of registry data as the ones available in Denmark provides this. By grouping psychiatry comorbidity according to ICD-10, mental illnesses with common pathways are analyzed together. In the ICD-10 system psychiatric diagnosis are grouped according to symptomatology and common etiology³⁰. All psychiatric diagnoses are considered relevant in the chosen population, as any psychiatric disorders represents a vulnerable patient with possible complicating factors when treating back pain. The limitation of Danish registry-based data is, that it does not provide complete data from the primary care sector selecting only severe psychiatric diagnosis. In conclusion, back pain disorders and the association with psychiatric comorbidity has primarily been investigated using symptomatology, not ICD-10 diagnoses and with a focus on anxiety and depression. The studies are small, heterogeneous and of varying quality. The use of pharmacological treatment, including opioids, in back pain disorders complicated by psychiatric comorbidity is unknown.

Aim of the thesis

The aim of this PhD thesis is to use population-based registry data to:

1) to estimate the prevalence of psychiatric comorbidity in patients with back pain disorders (BPD) compared to patients with no back pain in the time period 2010-2014; 2) Investigate whether presence of psychiatric comorbidity affects utilization of pharmacological, surgical and other types of treatment for patients with BPD 3) Investigate whether presence of psychiatric comorbidity affects utilization and dosages of pharmacological treatment for patients with BPD.

Clinical contributions of this PhD

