Information on somatic comorbidity for calculation of Charlson Comorbidity index³⁹ (CCI) at time of BPD diagnosis, will be retrieved from the DNPR. Data on psychiatric comorbidity will be identified using NPD-Psych. Information on marital status, vital status, and immigration status will be retrieved from the Civil Registration System (CPR)³⁵. Patients that are not alive or have emigrated within three years after BPD diagnosis are considered lost to follow-up and excluded from the cohort. Descriptive data on the socioeconomic status, education level and equivalent available income will be retrieved from Statistics Denmark³⁸. All data comprising each variable will be retrieved from 1th of January 2007 to 31th of December 2017 (three years before and after study period).

Measures of outcome: Primary outcome is to estimate prevalence of psychiatric comorbidity in patients with BPD compared to the Danish background population. Secondary outcome is to estimate prevalence of psychiatric comorbidity stratified by type of BPD (SBP UBP) compared to the Danish background population. We will use a presence of psychiatric comorbidity as outcome.

Statistics: We will use Fisher's exact test and t-test to compare baseline characteristics with 95% confidence intervals (CI) and p-values. Crude risks of psychiatric comorbidity will be calculated and logistic regression model will be used, to investigate differences between the distribution of risk in BPD patients and the background population. A logistic regression model will also be used to investigate differences between the distribution of psychiatric comorbidity in the IBD, DBD and UBP group compared to the background population. The logistic regressions will be reported using 95% CI and adjusted for the following confounders: age, sex, equivalent available income, educational level, CCI, marital status.

Study 2) The effect of psychiatric comorbidity on type of treatment for BPD

Aim: 1) To investigate whether treatment of BPD in patients with psychiatric comorbidity differ from treatment of patients with BPD without psychiatric comorbidity; 2) To investigate whether treatment of BPD differs in the following subgroups: a) specific BPD and no psychiatric comorbidity; b) specific BPD with psychiatric comorbidity; c) unspecific BPD with no psychiatric comorbidity; d) unspecific BPD with psychiatric comorbidity. Investigation will be performed in a nationwide Danish cohort in 2010-2014.

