Hypothesis: 1) Psychiatric comorbidity affects type of treatment in BPD patients and 2) psychiatric comorbidity affects type of treatment in subgroups of BPD.

Design and study population: The study will be a nationwide register-based cohort study. The study population consists of patients with BPD and in the sub-analysis the study population consists of patients with BPD and psychiatric comorbidity.

Procedure: BPD patients will be identified via the DNPR. Surgical treatment will be defined as the presence of any procedure code for back surgery retrieved from DNPR (NOMESCO: KNA-W)³⁴⁻⁴⁰. Pharmacological treatment of BPD will be defined as any treatment with the following drugs: NSAID (ATC: N01A*), acitomenophen (ATC: N02BE01), opioids (N02A*), antiepileptica (ATC: N03A) and tricyclic antidepressants (ATC: N06AA)¹³ identified using the Register of Medicinal Products Statistics⁷. Data on other types of treatment (defined as any treatment not surgical or pharmacological) such as physiotherapist, psychologist, chiropractor or occupational therapist (covered via tax-funded health insurance) will be obtained via The Danish National Health Insurance Service Register (SSR)³⁷. All BPD treatment-related information will be retrieved up to three years after the date of BPD diagnosis.

Information on somatic comorbidity for calculation of Charlson Comorbidity index³⁹ (CCI) at time of BPD diagnosis, will be retrieved from the DNPR. Data on psychiatric comorbidity will be identified using NPD-Psych. Information on psychiatric comorbidity will be used to define whether each patient had a psychiatric diagnosis prior to BPD diagnosis, after BPD diagnosis or no psychiatric diagnosis. If a psychiatric diagnosis occurs both prior to and after BPD diagnosis, the patient will be defined as having a psychiatric comorbidity prior to BPD diagnosis.

Information on marital status, vital status, and immigration status will be retrieved from the Civil Registration System (CPR)³⁵. Patients that are not alive or have emigrated within three years after BPD diagnosis are considered lost to follow-up and excluded from the cohort. Descriptive data on the socioeconomic status, education level and equivalent available income will be retrieved from Statistics Denmark³⁸. All data comprising each variable will be retrieved from 1th of January 2007 to 31th of December 2017 (three years before and after study period).

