Measures of outcome: The outcome is type of treatment for BPD (surgical, pharmacological and other types of treatment)

Statistics: We will use Fisher's exact test and t-test to compare patients' baseline characteristics with 95% confidence intervals (CI) and p-values. For each treatment type we will use logistic regression model to investigate differences in outcome distribution between patients with and without psychiatric comorbidity. The logistic regressions will be performed with 95% CI adjusted for the following confounders: age, sex, CCI, level of education, equivalent available income, type of BPD (IBD, DBD or UBP) and marital status.

Study 3) Effect of psychiatric comorbidity in pharmacological treatment of BPD.

Aim: 1) To compare dosages of pharmacological treatment in BPD patients with and without the presence of psychiatric comorbidity in a nationwide Danish cohort study in 2010-2014. 2) To compare high vs. low dosages of pharmacological treatment for BPD in patients with BPD and psychiatric comorbidity.

Hypothesis: 1) Patients with BPD and psychiatric comorbidity are prescribed a higher dosage of pain medication for BPD compared with BPD patients without psychiatric comorbidity. 2) BPD patients with a psychiatric comorbidity with a high (defined as above the 50th percentile) vs. low (defined as below the 50th percentile) dosage of pain medication are also prescribed higher dosages of psychiatric medication.

Design and study population: The study will be a nationwide register-based cohort study. The study population consists of patients with BPD that received pharmacological treatment for BPD. In the secondary analysis the study population consists of patients with BPD and a psychiatric comorbidity, who received pharmacological treatment for BPD.

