Procedure: BPD patients will be identified via the DNPR. Pharmacological treatment of BPD will be defined as any treatment with the following drugs: NSAID (ATC: N01A*), Acitomenophen (ATC: N02BE01), Opioids (N02A*)¹³. Pharmacological treatment for psychiatric comorbidity will be defined as any treatment with the following drugs: Antipsychotics (ATC:N05A), Antidepressants (ATC: N06A), Selective Serotonin Reuptake Inhibitors (SSRI) (ATC: N06AB), and anxiolytics (ATC: N5B*)⁴¹. Pharmacological treatment that can be used in the treatment of both BPD and psychiatric disorders will be defined as any treatment with the following drugs: Antiepileptics (ATC: N03A) and Tricyclic antidepressants (ATC: N06AA). All data on pharmacological treatment will be identified using the Register of Medicinal Products Statistics⁷. From time of BPD diagnosis and the following three years, pharmacological treatment for both somatic illness and psychiatric comorbidity in Daily Defined Dosage (DDD) per year will be calculated⁴².

Information on somatic comorbidity for calculation of Charlson Comorbidity index³⁹ (CCI) at time of BPD diagnosis, will be retrieved from the DNPR. Data on psychiatric comorbidity will be identified using NPD-Psych. Information on marital status, vital status, and immigration status will be retrieved from the Civil Registration System (CPR)³⁵. Patients that are not alive or have emigrated within three years after BPD diagnosis are considered lost to follow-up and excluded from the cohort. Descriptive data on the socioeconomic status, education level and equivalent available income will be retrieved from Statistics Denmark³⁸. All data comprising each variable will be retrieved from 1th of January 2007 to 31th of December 2017 (three years before and after study period).

Measures of outcome: Primary outcome is pharmacological treatment in DDDs defined as high (above the 50th percentile and low (below the 50th percentile) of pain medication. Secondary outcome is psychiatric medication in BPD patients with psychiatric comorbidity in DDD's defined according to high (above the 50th percentile) and low (below the 50th percentile) dosages of pain medication.

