Statistics: We will use Fisher's exact test and t-test to compare patients' baseline characteristics with 95% confidence intervals (CI) and p-values. Time dependent Cox regression will be performed separately for patients with specific and unspecific BPD to examine dosage of pharmacological treatment over time comparing patients with and without psychiatric comorbidity. The analysis will be performed with 95% CI and adjusted for the following confounders: age, sex, CCI, level of education, equivalent available income, marital status and the presence of psychopharmacological treatment.

To examine dosage of psychopharmacological treatment over time comparing patients with psychiatric comorbidity and low vs high dose of pharmacological treatment of BPD, time dependent Cox regression will be performed reporting 95% CI and adjusting for the following confounders: age, sex, CCI, level of education, equivalent available income, marital status.

Psychiatric comorbidity in Back Pain Disorders
Risk, treatment and pharmaco-epidemiological analysis

Ethics

All studies will be based on national clinical registries and approval is obtained by The Danish Health Data Board and the Danish Data Protection Agency (18/3337). According to Danish law, further ethical approval is not required for purely registry-based studies. All data will be stored on Statistics Denmark's servers and will be anonymized ensuring no patients can be identified.

PhD Outline

The PhD will be conducted within a timeframe of three years (six semesters).

	1st semester	2nd semester	3rd semester	4th semester	5th semester	6th semester
Data collection	X					
PhD Courses	X	X	X			
Data analysis		X	X	X	X	
Writing articles			X	X	X	X

References

1. Hawker GA. The assessment of musculoskeletal pain. *Clinical and experimental rheumatology* 2017;35 Suppl 107(5):8-12.

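### Study 2 counts antiepileptics (N03A) and tricyclics (N06AA) as back-pain treatment, Study 3 calls them dual-use; psychiatric prescribing may raise Study 2's drug odds ratio, and no analysis without them is planned

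*Combined protocol and SAP*

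**What the plan says.** **Study 2, Procedure.** Drug treatment of BPD means any treatment with an NSAID, paracetamol or one of these: "opioids (N02A*), antiepileptica (ATC: N03A) and tricyclic antidepressants (ATC: N06AA". Treatment data run for up to three years after the BPD diagnosis. No indication and no minimum amount is required.

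**Study 3, Procedure.** The same term is defined by a shorter list, "NSAID (ATC: N01A*), Acitomenophen (ATC: N02BE01), Opioids (N02A", which stops there. N03A and N06AA go into a separate category: "Pharmacological treatment that can be used in the treatment of both BPD and psychiatric disorders". The list of psychiatric drugs begins "Antipsychotics (ATC:N05A), Antidepressants (ATC: N06A".

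**Study 2, Aim and Statistics.** The first aim is "To investigate whether treatment of BPD in patients with psychiatric comorbidity differ from treatment of patients with BPD without psychiatric comorbidity". Each treatment type gets its own logistic model, adjusted for age, sex, Charlson index, education, income, "type of BPD (IBD, DBD or UBP) and marital status". Comorbidity is a psychiatric diagnosis from three years before to three years after the BPD diagnosis (Setting and study population).

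**Study 3, Statistics.** The Cox model for pain-drug dosage also adjusts for "marital status and the presence of psychopharmacological treatment".

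**Introduction.** On the Danish registry data, the plan concedes that "it does not provide complete data from the primary care sector selecting only severe psychiatric diagnosis".

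**The concern.** By the plan's own account in Study 3, N03A and N06AA may be prescribed for the kind of condition that defines exposure in Study 2. A patient who receives one of them only for a psychiatric disorder, and no other listed drug, is still counted in Study 2 as drug-treated for back pain. If this happens more often in comorbid patients, the misclassification of the outcome depends on exposure, and the odds ratio moves upward. The exposure and treatment windows overlap for three years, so timing does not separate the two uses. None of the Study 2 covariates bears on why a drug was prescribed.

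At stake is how Study 2's drug result is read. An odds ratio above 1 could mean more back-pain treatment or only more psychiatric prescribing, and true under-treatment of comorbid patients could be hidden. The surgical outcome does not use the drug lists and is not affected.

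**Working it through.** The plan states no expected odds ratio, prescribing rate or sample size, so there is no figure to reproduce. The calculation below only illustrates direction and possible size.

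**Inputs**
- b1, b0: share of comorbid and non-comorbid patients who qualify through pain treatment. Only 66% comes from the documents (Introduction, an upper figure for opioids alone). It is not the rate of the Study 2 outcome and serves as an illustrative base; 40% and 90% are assumed.
- p1, p0: share of the remaining patients who receive N03A or N06AA for a psychiatric disorder only. All values are assumed.

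**Formula.** Observed shares are a = b1 + (1 − b1)p1 and b = b0 + (1 − b0)p0. Observed OR = [a/(1 − a)] / [b/(1 − b)].

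**Worked case.** b1 = b0 = 0.66, p1 = 0.10, p0 = 0.02:
- a = 0.66 + 0.34 × 0.10 = 0.694, odds 2.268
- b = 0.66 + 0.34 × 0.02 = 0.6668, odds 2.001
- OR = 2.268 / 2.001 = 1.13, although the true OR is 1

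**No true difference**

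| p1 vs p0 | base 40% | base 66% | base 90% | base 66%, diluted |
|---|---|---|---|---|
| 2% vs 2% | 1.00 | 1.00 | 1.00 | 1.00 |
| 2% vs 1% | 1.03 | 1.02 | 1.01 | 1.01 |
| 5% vs 1% | 1.10 | 1.06 | 1.05 | 1.05 |
| 10% vs 2% | 1.22 | 1.13 | 1.10 | 1.11 |
| 20% vs 3% | 1.51 | 1.32 | 1.24 | 1.25 |

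The last column allows for psychiatric patients whom the registry misses and who therefore sit in the comparison group. It replaces p0 by 0.2·p1 + 0.8·p0, where the 20% is assumed. For 20% vs 3% this is 0.2 × 0.20 + 0.8 × 0.03 = 0.064, and the OR falls from 1.32 to 1.25.

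**True under-treatment, 61% vs 66%** (true OR 0.81). The observed OR is 0.92 at 10% vs 2% and 1.09 at 20% vs 3%. With p0 = 2%, the deficit disappears when p1 = 1 − (0.34 × 0.98)/0.39 = 14.6%. At 85% vs 90% (true OR 0.63), the same two pairs give 0.70 and 0.79, so the deficit stays visible.

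**The opposite bias when both classes are dropped.** Suppose true pain treatment is 66% in both groups, and 5% of comorbid vs 2% of other patients are treated for pain only with N03A or N06AA (assumed). The shorter list then sees 0.61 and 0.64, so OR = (0.61/0.39)/(0.64/0.36) = 0.88. At a 90% base it is (0.85/0.15)/(0.88/0.12) = 0.77. Here too the true OR is 1.

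**Study 3 codes.** By prefix, N06A contains N06AA, so tricyclics fall in both the psychiatric and the dual-use list. No rule gives precedence, and the plan does not say whether the dual-use classes count as psychopharmacological treatment.

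**The case against.** The difference between the lists may be deliberate. Study 2 asks whether a type of treatment was used; Study 3 compares doses, where setting dual-use drugs apart has an evident purpose. The plan itself says that these classes can treat BPD, so including them in Study 2 is defensible. This stands. What is shown is an unexplained difference with a foreseeable consequence; a reader might infer that the Study 2 list is simply wrong, but the documents do not support that.

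A reader might also infer that the drug odds ratio will be inflated. That requires psychiatric-only use to be more common among comorbid patients who have no other listed drug. This is plausible, but no rate is given. Incomplete capture of psychiatric cases would shrink the shift, as would a high share of patients on other listed drugs. Study 2's hypothesis is also non-directional, so the under-treatment cases are illustrations and not predictions of the plan.

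A third tempting inference is that the shorter list removes the problem and should be primary. It does not: it discards genuine pain use and can bias the result the other way. Nor would it help to adjust Study 2 for psychiatric drugs as Study 3 does. A covariate does not repair an outcome definition, and N06A would overlap with the outcome through N06AA.

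For Study 3, N06AB is also listed beside its parent N06A, so the nesting may be loose drafting. Study 3's pain-drug list itself excludes both dual-use classes.

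**Conclusion.** The point holds as a gap in outcome definition. Study 2's rule can record psychiatric prescribing as back-pain treatment, its exposure is psychiatric comorbidity, and nothing in the plan would show how much the result depends on this. The direction is upward if psychiatric-only use is clearly more common in comorbid patients. The size cannot be derived from the documents: at the illustrative 66% base, the assumed inputs give 1.02 to 1.32 when there is no true difference, and less if the comparison group contains unrecorded psychiatric cases. Neither the combined nor the shorter definition is free of bias. It should be fixed, with medium confidence, because the sponsor's own data can show whether it matters. The Study 3 overlap is a minor matter of definition, and no effect size is claimed for it.

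**What to change.** Before extraction:

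1. Reconcile the two lists, or state why the same term differs between Studies 2 and 3.
2. Name which Study 2 drug outcome is primary, and give the reason.
3. Report side by side, overall and in the four subgroups of Study 2's second aim: (a) the outcome without N03A and N06AA; (b) N03A and N06AA as a separate dual-use outcome; (c) the current combined outcome.
4. State that (c) can count psychiatric-only use and that (a) omits genuine pain use. If the conclusion changes between them, report it as uncertain.
5. Study 3 (minor): state whether N06AA and N03A count as psychiatric medication in the secondary outcome and in the psychopharmacological covariate.

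The cost is code-list edits and two extra logistic models per comparison, on data already requested, plus a less simple headline result. The Study 3 item needs only a sentence of definition.

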Psychiatric comorbidity will be defined as the presence of any of the following diagnosis, according to ICD-10 classification³⁰, obtained from the National Patient Registry – Psychiatry (NPD-Psych), covering all inpatient and outpatient psychiatric services in Denmark in the time period 1th January 2007 to 31th December 2017: Organic, including symptomatic, mental disorders (F00-DF09), Mental and behavioral disorders due to psychoactive substance use (F10-F19), Schizophrenia, schizotypal and delusional disorders (F20-F29), Mood [affective] disorders (F30-F39), Neurotic, stress-related and somatoform disorders (F40-F48), Behavioral syndromes associated with physiological disturbances and physical factors (F50-F59), Disorders of adult personality and behavior (F60-F69), Mental retardation (F70-F79), Disorders of psychological development (F80-F89), Behavioral and emotional disorders with onset usually occurring in childhood and adolescence (F90-F98) and, Unspecified mental disorder (F99). To qualify as a psychiatric comorbidity to back pain disorder, we define that the psychiatric diagnosis must be given no earlier than three years prior to back pain disorder diagnosis and no later than three years after.

Study 1) Prevalence of psychiatric comorbidity in back pain disorders

Psychiatric comorbidity in Back Pain Disorders
Risk, treatment and pharmaco-epidemiological analysis

Aim: 1) To estimate prevalence of psychiatric comorbidity in patients with BPD compared to patients without BPD and 2) To estimate prevalence of psychiatric comorbidity in patients with unspecific back pain (UBP) compared to the background population and to patients with a specific back pain (SBP) in a Danish nationwide cohort from 2010-2014.

Hypothesis: 1) There is a higher risk of psychiatric comorbidity in BPD patients compared to the background population and 2) UBP patients have a higher risk of psychiatric comorbidity compared to patients with specific BPD.

Design: The study will be a nationwide register-based matched cohort study.

Procedure: Selected BPD patients with the following diagnosis will be identified via the DNPR: Spondylopathies DM45-49, Other dorsopathies DM 50-54 and Segmental and somatic dysfunction DM99. Each patient will be matched 1:5 on age and sex with patients without back disorders by random at Statistics Denmark³⁸. The selection of diagnosis is to be able to match the population with non-BPD patients in the Danish registries.

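### Study 2's other-treatment outcome mixes psychologist contacts with back care and has no rule linking a contact to the back disorder, so its odds ratio can reflect psychiatric care

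*Combined protocol and SAP*

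**What the plan says.** The first hypothesis of Study 2 is that "Psychiatric comorbidity affects type of treatment in BPD patients". Under Measures of outcome the plan states: "The outcome is type of treatment for BPD (surgical, pharmacological and other types of treatment". The three types are not defined with equal care in Study 2, Procedure. Surgery is tied to procedure codes for back operations, and drug treatment to named ATC classes. The third type is a residual: "Data on other types of treatment (defined as any treatment not surgical or pharmacological) such as physiotherapist, psychologist, chiropractor or occupational therapist". The source of these contacts is limited to services "covered via tax-funded health insurance) will be obtained via The Danish National Health Insurance Service Register (SSR"), and the time limit is: "All BPD treatment-related information will be retrieved up to three years after the date of BPD diagnosis". No service-code list, referral reason or diagnosis links a contact to the back disorder.

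The exposure is defined under Setting and study population. Any ICD-10 F diagnosis counts, taken from the psychiatric patient register, "covering all inpatient and outpatient psychiatric services in Denmark". On timing, "the psychiatric diagnosis must be given no earlier than three years prior to back pain disorder diagnosis and no later than three years after".

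Under Study 2, Statistics: "For each treatment type we will use logistic regression model to investigate differences in outcome distribution between patients with and without psychiatric comorbidity". The model adjusts for demographic and socioeconomic variables, the Charlson index and type of BPD. No split by provider and no sensitivity analysis is planned.

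**The concern.** An outcome presented as treatment for BPD should rise or fall with how the back is treated. Psychologist care can be given for the exposure itself. A patient with a mood disorder who sees a psychologist for that disorder, and has no physiotherapy or chiropractic care, is scored as having received other BPD treatment.

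The timing makes this easier. The outcome window is the three years after BPD diagnosis, and a psychiatric diagnosis made in those same years still counts as exposure. One new psychiatric episode can supply both the exposure and the outcome. Study 2 does record whether the psychiatric diagnosis came before or after the BPD diagnosis, but the stated comparison is simply with against without comorbidity.

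The covariates cannot correct this. The problem lies in what the outcome counts, and no adjustment variable carries the reason for a contact. At stake is the meaning of one of Study 2's three results: a raised odds ratio could be read as more active back care, and a real shortfall in physical treatment among patients with psychiatric illness could go unseen.

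**Working it through.** The plan gives no rate, event count, sample size or power for Study 2, so there is no figure to reproduce. The check shows what the definition can do under stated assumptions.

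**Set-up.** Let p be the probability of physiotherapy, chiropractic or occupational therapy, and q the probability of a psychologist contact, taken as independent within each group. Subscript 1 means with psychiatric comorbidity and 0 without. The recorded proportion is

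P = 1 − (1 − p)(1 − q),

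and the recorded odds ratio (OR) is [P1/(1 − P1)] / [P0/(1 − P0)]. All values of p and q are assumptions.

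**Case A: no true difference (p = 0.50 in both groups, true OR 1.0; q0 = 0.05).**
- Without comorbidity: P0 = 1 − 0.50 × 0.95 = 0.525.
- q1 = 0.10: P1 = 1 − 0.50 × 0.90 = 0.55; OR 1.11.
- q1 = 0.20: P1 = 1 − 0.50 × 0.80 = 0.60; OR 1.36.
- q1 = 0.30: P1 = 1 − 0.50 × 0.70 = 0.65; OR 1.68.

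**Case B: a true deficit (p1 = 0.42, p0 = 0.50; q1 = 0.20, q0 = 0.05).**
- True OR for physical treatment: (0.42/0.58)/(0.50/0.50) = 0.72.
- Recorded: P1 = 1 − 0.58 × 0.80 = 0.536 against P0 = 0.525; OR 1.05. The deficit is no longer visible.

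**Case C: conditions that shrink the effect.**
- Physical treatment very common (p = 0.80 in both groups; q1 = 0.10, q0 = 0.05): P1 = 1 − 0.20 × 0.90 = 0.82, P0 = 1 − 0.20 × 0.95 = 0.81; OR 1.07.
- Equal psychologist use and equal physical treatment: OR 1.00.

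**Wider grid.** With p of 0.30, 0.50 and 0.70 and (q1, q0) of (0.05, 0.02), (0.10, 0.02), (0.20, 0.03) and (0.30, 0.03), a true OR of 1.0 is recorded as 1.04 (p = 0.70, first pair) to 2.20 (p = 0.30, last pair). With p0 = 0.50 and a true OR of 0.80, the four pairs give recorded ORs of 0.86, 0.96, 1.18 and 1.48. The deficit is diluted in the first two and reversed in the last two.

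**Would precision help?** No; a large cohort makes the artefact easier to declare significant. At p = 0.50, with a two-sided 5% test, 80% power and equal groups (all assumed), about 2,443 patients per group suffice for (0.10, 0.02), where the recorded proportions are 55.0% and 51.0%. About 535 per group suffice for (0.20, 0.03).

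**The case against.** Five points can be made for the plan.

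- **Psychological treatment is part of back care.** The Introduction lists cognitive-behavioral therapy among guideline-recommended interventions, so including psychologists looks deliberate. This stands. It rules out reading every psychologist contact as misclassified, and it argues against removing psychologists from BPD treatment altogether.
- **The registers differ.** Exposure comes from hospital psychiatry and the outcome from the SSR, so psychiatric care delivered in hospital does not enter the outcome. The Introduction also concedes that primary-care data are incomplete and that the psychiatric diagnoses captured are the severe ones. The group without comorbidity may therefore include people with milder disorders who also use SSR psychologists. This stands too. A reader might infer that the odds ratio is certainly biased upward, or that any non-surgical, non-drug service counts; the documents support neither. Higher psychologist use in the exposed group is plausible but not shown, and the exposure spans all F diagnoses, including organic and developmental disorders for which such care may be less usual.
- **The retrieval sentence speaks of BPD-related treatment information.** It does, but no rule puts that phrase into operation.
- **The aim could be read as utilization.** Aim of the thesis speaks of treatment utilization by patients with BPD, under which psychologist contacts are in scope for any reason. But Study 2's own aim and outcome refer to treatment of or for BPD. The two readings need to be reconciled.
- **Other providers share the gap.** Physiotherapy and occupational therapy contacts may also be for other conditions. True, but psychologist care is the named component most directly tied to the exposure.

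**Conclusion.** The point holds as a defect of definition. The other-treatment outcome is an open composite of SSR services, it names psychologist contacts, and it does not separate care for the back from care for the psychiatric disorder that defines the exposure. Its odds ratio can be biased upward and can hide lower use of physical treatment.

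The size is unknown. The figure of about 1.1 to 1.7 for a true odds ratio of 1.0 rests on three assumptions: 50% physical treatment in both groups, psychologist use of 10% to 30% against 5%, and independence of the two. Other inputs give less or more, and the effect is small if most patients have physiotherapy or chiropractic contacts anyway. The upward direction depends on SSR psychologist use being higher in patients with comorbidity.

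**What to change.** In Study 2, Procedure, replace the open residual with a closed list of SSR provider types: physiotherapist, chiropractor, occupational therapist and psychologist. In Study 2, Statistics:

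- fit the existing logistic model separately for each provider type;
- treat psychologist contacts as a dual-indication category, in line with the separate class that Study 3, Procedure already gives to drugs used for both BPD and psychiatric disorders;
- report the composite without psychologist contacts alongside the composite with them.

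This keeps psychologist-delivered back care visible while showing how far the composite depends on it. The cost is some protocol wording and a few more runs of the same model on data already requested. It does not establish the reason for any individual contact, so uncertainty about indication remains for the other provider types and should be stated as a limitation.
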